7.3 Withdrawal Visit

No early termination or withdrawal visits are anticipated, but in the event that this occurs, such a visit would follow the same guidelines established for a final study visit as long as the parent/caregiver is willing.

7.4 Unscheduled Visit

Although no unscheduled visits are anticipated, it is possible a participant may have a problem with the smartphone app, or Bluetooth toothbrushes and ask for study staff to help. Any such additional visits will be logged into REDCap. All adverse events will be reported as outlined in Section 9.

8 STUDY PROCEDURES /EVALUATIONS

8.1 Oral Examination Procedures

The clinical procedures and evaluations for this study will consist of the following: child's medical history will be evaluated via a self-reported standardized questionnaire administered to the parent/caregiver at the enrollment/baseline visit. A trained dental provider will perform the ASTDD BSS dental screening examination. Then, after applying disclosing solution, a study staff member will take photographs of anterior teeth with the study iPhone camera to record plaque levels. A central rater will determine a plaque score from an image of the facial (labial) surfaces of anterior teeth, following the Debris Index of the Simplified Oral Hygiene Index (OHI-S) modified for only the primary maxillary incisors (labeled the Debris Index of the Simplified Oral Hygiene Index for Maxillary Incisors and denoted as OHI-MIS). The OHI-MIS evaluator will be trained and calibrated as per CC protocol. Annually, the OHI-MIS evaluator will rerate 30 randomly selected photos during an intra-rater reliability plaque score calibration. After study staff demonstrate and observe parent/caregiver performance of study procedures, the dental provider will apply FV.

8.2 Focus Groups and Interviews

Four focus group discussions (FGDs) of approximately 10 people per arm will be conducted in English and Spanish after the Month 6 visit. Two FGDs of intervention arm participants (one in English and one in Spanish) will be conducted after the Month 12 visit. Participants will be chosen based on study performance (e.g., above and below high and low thresholds of toothbrushing performance). Each FGD session will be about 45-60 minutes in duration. The FGDs will focus on topics related to participants' involvement in the intervention: oral health behaviors and health habits, dental care motivation behavior, toothbrushing and reactions to the powered toothbrush, toothpaste pump use, toothbrush syncing, Sonicare app use, text message reminders, opportunity

costs, incentives, overall satisfaction, and perspectives on behavior data tracking for personal use and outside monitoring purposes. Semi-structured discussion guides will be developed and refined for comprehension, relevancy, and appropriateness prior to conducting all interviews. Participants will receive a \$30 grocery store gift card for their time and participation.

In addition, 6 to 12 stakeholder interviews will be conducted with EHS and affiliated day care center staff after the Month 6 visit. Semi-structured interview guides will be refined for comprehension, relevancy, and appropriateness prior to conducting all interviews. Topics include how stakeholders were involved in executing the intervention, perceptions of the value the intervention added for the population served, the most challenging aspect for their organization, and recommendations for improvements. Based on prior feedback, stakeholders (staff) will receive a retailer gift card.

8.3 Questionnaires

Research staff will administer CAPI questionnaires to parents/caregivers during each study visit, with data entered directly into the EDC; questionnaire data will be analyzed for changes in self-reported behaviors and perceptions, including relevant common data elements (CDEs) identified by the Oral Health Disparities Consortium Collaborative Working Groups. Questionnaire items include demographics, behavioral beliefs (e.g. current brushing behaviors, dental visit attendance), normative beliefs (e.g. peer comparisons), control beliefs (e.g. motivation, and self-efficacy) from BRFQ (Albino et al., 2017), economic module (time preferences, risk preferences, ambiguity aversion, numeracy, overconfidence, and limited attention/memory), and Early Childhood Oral Health Impact Scale (ECOHIS) (Pahel et al. 2007). Follow-up questionnaires will assess satisfaction/acceptance of the incentives and study procedures, as well as adherence with study procedures, such as whether others in the household used the child's powered toothbrush or TP pump.

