3.2.2 Secondary

Intermediate toothbrushing performance measures are as follows:

- Mean of the number of qualifying half-day toothbrushing episodes per week, through 1 month for short-term effects
- Mean of the number of qualifying half-day toothbrushing episodes per week, through the Month 3 visit for mid-term effects after any novelty effect would be expected to end,
- Mean of the number of qualifying half-day toothbrushing episodes per week, from Month 6 visit to Month 12 visit for longer-term effects

For the outcomes listed above, the minimum qualifying length of time is 1 minute.

Additional secondary oral health measures will be ascertained:

- Debris Index of the Simplified Oral Hygiene Index for Maxillary Incisors (OHI-MIS) to measure plaque on primary maxillary incisor facial (labial) tooth surfaces at Month 6 and Month 12 visits (mean of 4 ordinal scores)
- TP pump weight change (grams) at Month 6 and Month 12 visits
- Binary measure of Association of State and Territorial Dental Directors Basic Screening Survey (ASTDD BSS) untreated caries status ($dt>0$) at Month 6 and Month 12 visits
- Binary measure of ASTDD BSS caries experience status ($dmft>0$) at Month 6 and Month 12 visits; m is missing due to caries only
- Binary measure of ASTDD BSS severe caries ($dmft 4+$) status at Month 6 and Month 12 visits; m is missing due to caries only
- Binary measure of a dental visit in the past 12 months, obtained through EHS ChildPlus database which records annual dental visit and other required health screenings

To assess potential mediation effects of beliefs (behavioral, normative, and control) on intermediate outcomes (intentions, salience, and habit) and primary outcome (toothbrushing performance), the aforementioned primary and secondary outcome measures will be assessed. Behavioral, normative, and control beliefs will be collected via the BRFQ at each study visit (see Section 8.3). Intentions, salience, and habit will be collected with components of the BRFQ (e.g. intentions to brush child's teeth in the next 6 months, preventive habits for one's self and for one's child, age started brushing study child's teeth.).

To estimate the short- and long-term cost effectiveness and return on investment of rewards in improving parent/caregiver behaviors and children's oral health, net costs will be ascertained (as detailed in Section 12.4).

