7.1.2 Baseline (Post-Run-In/Randomization) Visit (Visit 2, $T = 0$ [+10/-2])

- Administer CAPI questionnaire to parent/caregiver.
- Click the REDCap “randomize” button to reveal participant’s randomized assignment to arm. Explain the intervention procedures and rewards program (if assigned to the Intervention Arm) to the parent/caregiver and have her/him explain it back in her/his own words. Explain control procedures (if assigned to the Control Arm) to the parent/caregiver and have her/him explain it back in her/his own words.
- Schedule the family’s next visit (in approximately 3 months) and give the parent/caregiver \$30 compensation for attending the baseline visit.

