To investigate the behavioral economics mechanisms through which behavior change outcomes may have operated, **mediation analyses** will be conducted with the measures of risk preferences (i.e., for the presence of prospect theory tendencies), time preferences (i.e., for the presence of present bias), and forgetfulness (i.e., for attention). Each of these factors will be investigated in separate models to assess the extent the particular underlying construct lies within the pathway toward toothbrushing behavior change (i.e., by reducing the estimate of the ITT main effect).

In addition, because parents and children with different backgrounds (e.g., child's age, parent's/caregiver's education) and behavioral, normative, and control beliefs may respond differently to the incentives given, heterogeneity of treatment effect analyses will be conducted to identify groups influenced by the intervention. For example, the UH2 pilot (White *et al.* 2020) suggested the intervention on toothbrushing frequency may vary by child age (<24mo vs \geq 24mo). The results of these analyses will also inform the sampling frame for the parent FGDs so that important dimensions of diversity can be represented.

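### The mediation rule in Section 12.4 omits pre-randomisation construct values and run-in brushing, so its result is biased if the rewards move a construct that relates to brushing for other reasons

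*Combined protocol and SAP*

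**What the plan says.** Section 3.1.2 makes mediation a secondary objective, with beliefs as the mediators. The only model is in Section 12.4, and it covers a different set of constructs: "mediation analyses will be conducted with the measures of risk preferences", together with time preferences and forgetfulness. The rule is: "Each of these factors will be investigated in separate models to assess the extent the particular underlying construct lies within the pathway". The stated sign of mediation is that the construct acts "by reducing the estimate of the ITT main effect". The section does not say at which visit the construct is taken. It names no covariate, no baseline value of the construct and no baseline brushing. Baseline characteristics enter 12.4 only for heterogeneity of treatment effect.

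Pre-randomisation data exist:

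- **Beliefs.** Section 3.2.2: "Behavioral, normative, and control beliefs will be collected via the BRFQ at each study visit".
- **Questionnaire timing.** Section 7.1.2 lists "Administer CAPI questionnaire to parent/caregiver" ahead of the randomisation step, and Section 7.1.1 has a questionnaire at screening as well.
- **Economic constructs.** Section 8.3 lists an "economic module (time preferences, risk preferences, ambiguity aversion, numeracy, overconfidence, and limited attention/memory" set of items. It does not tie them to particular visits beyond the general statement "Research staff will administer CAPI questionnaires to parents/caregivers during each study visit".
- **Run-in brushing.** Sections 4 and 6.2 give two weeks of synced brushing without performance rewards. Section 4 puts randomisation after the run-in and does not randomise dyads who cannot supply run-in data.

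**The concern.** Comparing the group coefficient with and without a construct estimates an indirect effect only if nothing else links the construct to brushing. Randomisation makes the reward-to-construct comparison fair. It does nothing for the construct-to-brushing association within an arm. If, say, less forgetful parents brush more in either arm, a post-randomisation forgetfulness score carries that standing difference. Should the rewards also shift the score, the model credits the shift with the standing association, even if the shift changed no brushing.

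At stake is the explanation of why rewards work. A construct that merely marks who brushes anyway could be reported as a mechanism, or a real mechanism could be masked if the signs oppose. The pre-randomisation construct value and run-in brushing are the obvious measures of those standing differences, and the plan gives neither a role.

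**Working it through.** **The plan's own figure.** Section 12.2 states 84% power for 91 per group, difference 2.65, SD 6.0, two-sided 5%. The noncentral t gives 84.2%, so it reproduces. The documents give no figure for mediation.

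**Inputs.** From 12.2: effect 2.65 and SD 6.0, so the standardised effect is 2.65/6.0 = 0.4417. Assumed, because the documents give no values:

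- reward shift in the construct, a = 0.1 to 0.5 SD
- within-arm correlation of construct (either occasion) with brushing (either occasion), c = 0.2 to 0.4, none of it causal
- test-retest correlation of the construct, r = 0.7
- correlation of run-in with outcome brushing, q = 0.6 or 0.3

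True mediation is zero throughout.

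**Formula.** Group is independent of the baseline covariates. The expected fall in the group coefficient is therefore a × b, where b is the construct's standardised partial coefficient. The false mediated share is a × b / 0.4417. Solving the normal equations:

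- no covariates: b = c
- run-in brushing only: b = c(1 − q)/(1 − c²)
- baseline construct only: b = c/(1 + r)
- both: b = c(1 − q)/(1 + r − 2c²)

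| Model | a = 0.1, c = 0.2 | a = 0.5, c = 0.4 |
|---|---|---|
| None | 0.1 × 0.2/0.4417 = 4.5% | 0.5 × 0.4/0.4417 = 45.3% |
| Baseline construct | 4.5%/1.7 = 2.7% | 45.3%/1.7 = 26.6% |
| Both, q = 0.6 | b = 0.08/1.62 = 0.0494; 1.1% | b = 0.16/1.38 = 0.1159; 13.1% |
| Both, q = 0.3 | b = 0.14/1.62 = 0.0864; 2.0% | b = 0.28/1.38 = 0.2029; 23.0% |

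Simulation at these settings gave about 4% to 46% unadjusted, in line with the formula. In episodes per week (a × b × 6.0), the unadjusted range is 0.12 to 1.2.

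**Separate simulation** (91 per arm, 4,000 runs, test-retest 0.7, stable share of brushing variance 0.5 to 0.7, correlation of stable parts 0.3 to 0.5):

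- Shift 0.2 SD: 8–16% unadjusted, 5–9% with the baseline construct, 2–4% with both.
- Shift 0.4 SD: 16–32%, 10–19% and 5–9%.
- No shift: mean false share within 0.1% of zero in every model. Adding both baselines still cuts the SD of the estimate from 0.17–0.32 to 0.07–0.08 episodes per week, and the chance of a drop above 10% from 7–18% to about 1%.

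**Opposite sign.** At a = −0.3 the unadjusted share is −0.3 × 0.2/0.4417 = −13.6% to −0.3 × 0.4/0.4417 = −27.2%. The ITT estimate rises.

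**The case against.** The strongest case against has five parts.

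1. **Stable differences alone do no harm on average.** A reader might infer that differences between parents are by themselves counted as reward mechanisms, or that any shift in the construct makes the ITT estimate fall. Neither follows. Randomisation balances the differences; without a shift the mean bias is about zero, and with a shift of opposite sign the estimate rises. This stands, and the point is limited accordingly.
2. **The size rests on assumed shifts.** Nothing in the documents says that a weekly drawing moves risk or time preferences by 0.5 SD. At 0.1 SD the unadjusted share is only about 4% to 9% (0.1 × 0.4/0.4417 = 9.1%). This stands: the upper end needs two assumptions at their maximum together. Still, Section 2.2 itself suggests that rewards raise salience and offset limited attention, so a shift in at least some constructs is part of the trial's theory.
3. **Silence is not a decision.** Section 12.4 does not say that baselines are excluded, and 8.3 plans to analyse changes in questionnaire data. True, but 8.3 does not link this to mediation, and 12.4 does state a concrete rule. A pre-randomisation value cannot have been moved by the reward, so the rule only makes sense with a post-randomisation value.
4. **Baseline collection of the economic module is implied, not stated.** The visit-specific questionnaires are separate documents. This stands as something to confirm. Beliefs and run-in brushing are explicit.
5. **Run-in brushing may predict poorly.** It covers the first two weeks with a powered brush, inside the roughly 12-week novelty period described in 2.1. This stands, which is why the result for a correlation of 0.3 is given beside 0.6.

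**Conclusion.** The concern holds in a conditional form. The stated rule gives a biased mediation result whenever the rewards move a construct that correlates with brushing for non-causal reasons, and the sign of the bias depends on the two directions. Over the assumed ranges, with shift and association in the same direction, the false share is about 4% to 46% unadjusted. With both baselines it is about 1% to 13% or about 2% to 23%, depending on how well run-in brushing predicts later brushing. These ranges show direction and rough size only. The sample size does not drive the mean bias; it affects the noise.

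Adjustment reduces the bias but does not remove it. Nor do the documents support any wider claim: the primary comparison and its power are untouched. The belief mediators of 3.1.2 cannot be said to be analysed wrongly, because they have no model at all. That is a gap to fill in the same edit. This should be fixed, for a secondary objective.

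**What to change.** In Section 12.4:

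1. State the visit at which each mediator is taken.
2. Fit the models with and without the post-randomisation construct using the same covariates: mean weekly qualifying episodes in the run-in, and the pre-randomisation value of that construct. Estimate the indirect effect from that pair.
3. Apply the same specification to the belief mediators of 3.1.2.
4. Confirm that the economic module is asked before randomisation. If it is not, adjust for run-in brushing alone and say so. Under the same assumptions that leaves about 2% to 22% at a run-in correlation of 0.6 (b = 0.08/0.96 and 0.16/0.84), or 3% to 38% at 0.3 (b = 0.14/0.96 and 0.28/0.84).
5. State that residual confounding between construct and brushing remains, ideally with a sensitivity analysis.

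The cost is wording and two covariates, with no new data collection for beliefs or brushing. A few dyads missing a baseline item would need the multiple imputation that 12.4 already plans for sensitivity analyses.

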8.4 Anticipatory Guidance

A short health education video in English or Spanish will provide parents/caregivers with key preventive oral health messages appropriate for the child's age, such as the importance of fluoride supplements, healthy snacking and how to prevent the spread of bacteria that causes caries.

8.5 Toothbrushing Performance and Frequency

8.5.1 Smart Toothbrushes

During the baseline visit, all participants will receive a "smart" powered toothbrush (e.g., Philips Oral Healthcare). The toothbrush uses Bluetooth technology to transmit data on brushing timing, frequency, and duration from the toothbrush to an app installed on the

participant's smartphone. The vendor (i.e., Philips Oral Healthcare) has provided a script which the Coordinating Center has scheduled to run weekly to securely transmit coded (indirectly identifiable) participants' brushing data to REDCap.

8.6 Dental Visit Attendance

For children enrolled at an EHS, preventive dental visit attendance of participating children will be ascertained through dental exam data from Head Start's ChildPlus Management Software health module at baseline and the Month 12 follow-up. In addition, for all children, parents will be asked about the date of the last dental visit within the baseline and Month 12 follow-up questionnaire.

8.7 Study Products

The Project Manager will maintain a log of disclosing solution, FV, and TP shipments, including batch numbers and expiration dates. The study products will be stored in the Project Manager's office at UCLA.

8.7.1 Plaque Disclosing Solution

At the baseline, Month 6, and Month 12 follow-up visits, the dental provider will apply Henry Schein Reveal Liquid plaque disclosing agent to the child's teeth with a microbrush for OHI-MIS plaque assessment.

8.7.2 Fluoride Varnish

Vanish Fluoride Varnish (3M) is a varnish that is applied to the teeth and enhances enamel acid and boosts salivary fluoride levels. The product contains fluoride, calcium and phosphate (but not CPP-ACP), which helps the product remain on the teeth longer and provides extra protection. Vanish Fluoride Varnish can be applied quickly without color change to the teeth. A dental provider will apply the fluoride varnish with a microbrush.

8.7.3 Fluoride Toothpaste Pump

Study participants will be instructed to use fluoridated TP based on the recent ADA consensus guideline (2014) that recommends all children use fluoride TP to help prevent dental disease. The study will use Colgate Maximum Cavity Protection Pump Fluoride Toothpaste (Colgate-Palmolive Company) (mild bubble fruit flavored).

The parents/caregivers will be instructed on how to dispense a smear or pea-sized amount (depending on child's age) of fluoride TP onto the toothbrush for the child, as per study guidelines.

If a child experiences an adverse reaction to the fluoride TP, he/she will be provided clinical guidance (e.g., discontinue use of the product); based on clinical judgment and appropriate input from oversight groups, use may be re-started. However, no modification of study product dosage will be made.

8.8 COVID-19 Modifications

The COVID-19 pandemic resulted in “stay at home” orders in Los Angeles county, causing the BEECON study move to remote/telephonic visits starting on 16 March 2020. Starting 01 October 2020, in accordance with state, county, UCLA, and community health center guidance, the Venice Family Clinic allowed BEECON to resume in-person visits. BEECON will continue to utilize a hybrid of remote/telephonic visits and conducting in-person dental screens as the clinic and public health guidelines allow.

9 ASSESSMENT OF SAFETY

9.1 Specification of Safety Parameters

The Principal Investigator (PI) will report safety events for the study (unanticipated problems [UPs], adverse events [AEs], serious adverse events [SAEs]) to the Institutional Review Board (IRB) in accordance with the IRB’s requirements.

The PI will also report UPs involving risks to subjects to NIDCR. This will include UPs that meet the definition of a SAE. AEs that are temporally associated with the administration by study personnel of FV will be recorded in an adverse event log, and this log will be monitored to identify events that meet the definition of a UP. If a UP is identified, it must be reported.

9.1.1 *Unanticipated Problems (UPs)*

The Office for Human Research Protections (OHRP) considers unanticipated problems (UPs) involving risks to subjects or others to include, in general, any incident, experience, or outcome that meets **all** of the following criteria:

- Unexpected in terms of nature, severity, or frequency given (a) the research procedures that are described in the protocol-related documents, such as the IRB-approved research protocol and informed consent document; and (b) the characteristics of the subject population being studied;
- Related or possibly related to participation in the research (“possibly related” means there is a reasonable possibility that the incident, experience, or outcome may have been caused by the procedures involved in the research); and

- Suggests that the research places subjects or others at a greater risk of harm (including physical, psychological, economic, or social harm) than was previously known or recognized.

9.1.2 Adverse Events

OHRP defines an adverse event as any untoward or unfavorable medical occurrence in a human subject, including any abnormal sign (for example, abnormal physical exam or laboratory finding), symptom, or disease, temporally associated with the subject's participation in the research, whether or not considered related to the subject's participation in the research (modified from the definition of adverse events in the 1996 International Conference on Harmonization E-6 Guidelines for Good Clinical Practice).

AEs will be recorded in REDCap, and the PI will monitor these events to grade severity, relationship to the study product, and assess whether the nature, severity, frequency is unexpected, and thus warrants reporting as a UP.

